#### Secondary

- To calculate the specimen volume after BCL guided partial mastectomy;
- To evaluate the surgeon's perception of ease of use of the BCL System;
- To evaluate the safety and tolerability of BCL;
- To evaluate the patient's satisfaction.

	Study Title	An Interventional, Post-Market Study to Evaluate the Performance of a Custom-made Medical Device, "Breast Cancer Locator Guidance (BCL)" System, in Breast-conserving Surgery (BCS)		
	Study ID	CS-BCL-EU2021	Sponsor	CairnSurgical Inc.
	Date	25Nov2022	Version	1.0 Substantial Amendment 1_GERMANY

## 2.3 STUDY ENDPOINTS

### 2.3.1 Primary Endpoints

To evaluate the performance of BCL in reducing the positive margin rate, the proportion of patients with positive margins after partial mastectomy with the BCL, will be obtained (results will be available within 14 days from the day of sample arrival at the pathological lab).

### 2.3.2 Secondary Endpoints

- To calculate the specimen volume after BCL guided partial mastectomy, the water displacement method (WDM) will be used (results will be obtained within the same day of surgery).
- To evaluate the surgeon's perception of ease of use of the BCL System, a 5 Likert scale will be used at V2;
- To evaluate the safety and tolerability of BCL through physical examination and AEs assessment including the relationship of the AE to the BCL System at V1, V2, V3, V4;
- To evaluate the patient's satisfaction, the BREAST-Q will be used at EOS/V4.

### 2.3.3 Study Early Termination

Early termination or suspension of the study is not anticipated. The Sponsor reserves the right to terminate an investigational site from the study for any of the following reasons:

- Failure to comply with investigational plan;
- Failure to obtain written informed consent from Subjects;
- Failure to provide case report forms and/or source documentation;

If the study is terminated early, the Investigator should consult with the Subjects enrolled to determine appropriate follow-up and subsequent treatment. After the end of the study the investigator will ensure the treatments and the support required as per clinical practices. All study data obtained prior to the study termination should be provided to the Sponsor.

## 2.4 BIOLOGICAL SAMPLES MANAGEMENT

All biological samples (blood samples and tumor specimens) collected according to the Laboratory Manual will be managed according to site internal procedures but ensuring the maintenance of the correspondence between samples and number assigned to the enrolled patient.

At the end of the study, after concluding all the analysis planned in the trial, all the biological samples stored as per Laboratory Manual will be destroyed, as per site procedure. They will be processed exclusively for the analysis described in this study and according to the trial procedures.

	Study Title	An Interventional, Post-Market Study to Evaluate the Performance of a Custom-made Medical Device, "Breast Cancer Locator Guidance (BCL)" System, in Breast-conserving Surgery (BCS)		
	Study ID	CS-BCL-EU2021	Sponsor	CairnSurgical Inc.
	Date	25Nov2022	Version	1.0 Substantial Amendment 1_GERMANY

## 2.5 STATISTICAL METHODS AND DATA ANALYSIS

### 2.5.1 Sample Size Justification

The positive margin rate (PMR) rate with the use of BCL is expected to be < 5% based on our previous study [20]. If we assume a true PMR rate of 3% and applying the exact or Clopper-Pearson method for a single binomial proportion then a sample size of N=35 will achieve a confidence interval with total width of 15%. The upper limit of this confidence interval (18%) is lower than the currently observed positive margin rate using the standard of care.

We will calculate an exact binomial confidence interval using the actual PMR.

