Background and Rationale:	
Breast cancer (BC) is the most commonly diagnosed cancer and leading cause of cancer-related death among women. Breast cancer screening programs and improved imaging techniques have contributed to an increased incidence of early-diagnosed (non-palpable) invasive breast cancer (IBC) or ductal carcinoma in situ (DCIS).
 
Breast conserving surgery (BCS), also known as lumpectomy or partial mastectomy, can be considered the gold standard of early stage invasive breast cancer treatment. The primary aims of BCS are 1) to resect the tumor with a surrounding margin of tissue free of cancer cells and 2) to minimize the volume of tissue removed, thereby preserving the overall shape and appearance of the breast. Consequently, BCS results in better physical and psychological well-being when compared to mastectomy procedure. One of the challenges of BCS in non-palpable breast cancer is precise localization of the tumor. The standard method for localization of non-palpable breast lesions is wire-guided localization (WGL) which consists of ultrasound or mammography assisted introduction of the guide wire allowing accurate location of the tumor. Despite the safety and cost-effectiveness of WGL, several complications have been reported included vasovagal reactions, cutting, moving, or loss of the wire, and patient discomfort. Furthermore, WGL may result in excessive removal of breast tissue (therefore, inferior cosmetic outcomes) and high positive margin rates leading to re-operation or an increased risk of local recurrence.
 
CairnSurgical has developed the Breast Cancer Locator (BCL) System. Within the BCL procedure, a supine MRI image is first performed with the breast positioned in its surgical position providing precise detail on the size, shape, depth, edges and 1 centimeter margin for the tumor. These data are then used to analyze the tumor and construct a three-dimensional (3D) tumor model that serves as the basis for two surgical tools. The MRI is also used to manufacture the BCL, a 3D-printed bra-like plastic form that matches the breast surface and designed to guide the surgeon to the precise tumor boundaries and margins. The BCL is constructed pre-operatively, sterilized, packaged and shipped to the hospital of the surgeon prior to the day of the procedure.
 
Dartmouth-Hitchcock Medical Center investigators have recently completed a randomized prospective clinical trial comparing supine MRI, intraoperative scanning and tracking technique to wire localization. One hundred thirty eight (138) subjects were randomly assigned in a 1:1 ratio to partial mastectomy guided by supine MRI or wire localization. The proportion of subjects with positive margins in the MRI guided surgery group was half that observed in wire localization group (9% vs. 19%, <math>p = 0.08</math>).
	

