	
enroll patients who require the tumor to be localized in order for the surgeon to perform BCS. The investigation will be useful to collect Investigational Product (IP)' performance/safety evidence in Europe.
 
Each Subject, after signing the Informed Consent Form (ICF), will enter into a screening phase (V0) during which several assessments (e.g., demographics, medical history, evaluation of available prone MRI and core biopsy pathological results) will be conducted. Blood samples will be collected at V0.
 
At visit 1 (V1), the Subject will undergo supine MRI (10-40 days prior to surgery), from which the 3D breast image and BCL will be made. At visit 2 (V2) the patient will undergo BCS using the BCL system.
 
Soon after surgery and prior discharge, potential AEs will be assessed. On the same day, the specimen volume will be determined. The excised specimen will be sent to the pathological lab for analysis. The results, including the positive margin rate (PMR) and specimen mammogram, will be obtained within 14 days.
 
At visit 3 (V3), follow-up assessments (including physical examination, and AEs review) will be performed. At the End Of Study (EOS/V4), AEs events will be assessed and patients will be asked to express their satisfaction with the BREAST-Q.
		
Study Population:	Adult women with a diagnosis by pre-operative biopsy of non-palpable breast cancer.		
Number of subjects (planned and analysed):	Planned:	35 subjects will be enrolled.	
	Sample size justification:	
The positive margin rate (PMR) rate with the use of BCL is expected to be < 5%. If we assume a true PMR rate of 3% and applying the exact or Clopper-Pearson method for a single binomial proportion then a sample size of N=35 will achieve a confidence interval with total width of 15%.
 
We will calculate an exact binomial confidence interval using the actual PMR.
	
	Safety Set	The "Safety Set" included all enrolled patients undergoing surgery with the BCL system.	
	Full Analysis Set (FAS)	The "Full Analysis Set" (FAS): this set included all enrolled patients undergoing surgery with the BCL system.	
	Per protocol Set (PPS)	The "Per-Protocol Set (PPS)" would include all the FAS patients who (a) met all inclusion/exclusion criteria liable to affect the performance assessment, (b) did not present serious deviations of the protocol that may affect efficacy.	

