### 2.5.2 Data Analysis

In general, all the variables will be descriptively analysed by visit (mean, median, standard deviation, minimum and maximum for continuous variables after normality check of distribution with Kolmogorov-Smirnov test, frequency distribution for categorical variables).

In particular, for the primary analysis PMR will be calculated when results of histopathological examination will be provided (results will be available within 14 days from the day of sample arrival at the pathological lab).

Moreover, 95% Confidence Interval (CI) of PMR will be presented.

All secondary endpoints will be evaluated in a descriptive way presenting the results by study visit, where appropriate.

All the analysis will be detailed in the Statistical Analysis Plan (SAP) which will be finalized in Version 1.0 before the Data Base Lock (DBL).

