Barth et al., have recently completed a randomized prospective clinical trial comparing *supine* MRI, intraoperative scanning and tracking technique to wire localization [23]. The study involved one hundred thirty-eight (138) subjects randomly assigned in a 1:1 ratio to partial mastectomy guided by *supine* MRI (group MRI) or wire localization (group WL). Sixty-six (66) percent had invasive breast cancer and DCIS, 22% had invasive cancer and 12% had DCIS. No differences in subject or tumor characteristics existed between groups. The proportion of subjects with positive margins in the MRI guided surgery group was half that observed in group WL: 12% vs. 23% ( $p = 0.08$ ). Mean specimen volumes in groups MRI and WL were not significantly different: 74 vs. 70 ml ( $p = 0.45$ ). Margins for invasive cancers were considered positive if invasive cancer or DCIS cells were present at the edge (on ink) or if DCIS was present  $< 1$  mm from the inked edge. Margins for specimens that contained only DCIS were considered positive if DCIS was present  $< 1$  mm from the inked edge. Consensus guidelines for positive margins were established after the study was initiated [24], [25]. The consensus guideline criteria for a positive margin for invasive cancer was invasive cancer or DCIS at the edge (on ink); the margin for cases that contained only DCIS was considered positive if DCIS was present  $< 2$  mm from the inked edge. Using the new consensus definition of positive margins, the positive margin rate in the MRI group (9%) was lower than those reported in any previously published RCT.

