#### Analysis of Primary Efficacy variable:

To evaluate the performance of BCL in reducing the positive margin rate, exact . 95% Confidence Interval (CI) for positive margin rate (PMR) using the Clopper-Pearson method will be estimated with actual positive margin rate calculated at V2

The primary analysis will be performed on both FAS and PPS. The analysis performed on PPS will be obtained to support the results on FAS.

Moreover, bar plots will be presented to show the positive margin rate distribution.

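### The 18% upper confidence limit in the sample size justification should be about 15%; the 15% width is right, and N=35 and the comparison at a 3% rate still hold

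*Protocol*

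**What the plan says.** Protocol 2.5.1 expects a positive margin rate below 5% and plans on 3%: "If we assume a true PMR rate of 3% and applying the exact or Clopper-Pearson method for a single binomial proportion". From this it concludes that "a sample size of N=35 will achieve a confidence interval with total width of 15" percent, and adds: "The upper limit of this confidence interval (18%) is lower than the currently observed positive margin rate using the standard of care". SAP 1.2.3 repeats the sentence with the same 18%. The protocol synopsis gives the width but neither the 18% nor the comparison with standard of care.

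The confidence level comes from the analysis sections. Protocol 2.5.2 says "Moreover, 95% Confidence Interval (CI) of PMR will be presented", and SAP 6.2.1 says "95% Confidence Interval (CI) for positive margin rate (PMR) using the Clopper-Pearson method will be estimated".

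Neither sample size section gives the standard-of-care rate. Elsewhere the protocol reports the 138-subject randomized trial of supine-MRI-guided against wire-localized surgery in two ways:

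- The synopsis (Background and Rationale) says the MRI-guided rate was "half that observed in wire localization group (9% vs. 19" percent.
- Section 2.11.1 says it was "half that observed in group WL: 12% vs. 23" percent.

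Both pairs carry p = 0.08.

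**The concern.** The two printed figures cannot both be right. If the total width is 15% and the upper limit is 18%, the lower limit is 18% − 15% = 3%, which is the assumed rate itself. A two-sided exact interval does not start at its own point estimate.

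The sentence matters because it is the only place where either document's statistical text sets the design against standard of care. The study has one arm, and its primary objective is worded as reducing the positive margin rate. A reader who wants to know what N=35 can show will look here. That reader finds a limit that does not follow from the stated inputs, and a comparator with no value, source or margin definition.

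**Working it through.** **Inputs.** Assumed rate 3%, N = 35 and the Clopper-Pearson method (Protocol 2.5.1, SAP 1.2.3); 95% level (Protocol 2.5.2, SAP 6.2.1). The level is taken as two-sided because a total width is quoted. Candidate comparators are 19% (synopsis) and 23% (Protocol 2.11.1).

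**Formula.** With x positives in n patients and B(q; a, b) the q-quantile of the beta distribution:

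- lower = B(0.025; x, n − x + 1)
- upper = B(0.975; x + 1, n − x)

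**The plan's own case.** A rate of 3% in 35 is 1.05 expected positives, so both the nearest whole count and the exact 3% are shown.

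| Case | Lower | Upper | Width |
|---|---|---|---|
| x = 1 (2.86%) | B(0.025; 1, 35) = 0.07% | B(0.975; 2, 34) = 14.92% | 14.84 points |
| x = 1.05 (3.00%) | B(0.025; 1.05, 34.95) = 0.09% | B(0.975; 2.05, 33.95) = 15.14% | 15.05 points |

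The stated 15% width reproduces and the stated 18% does not. Because the lower limit is below 0.1%, the width and the upper limit must be almost equal.

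**Could another method give 18%?** At exactly 3% or 1/35, the upper limits are:

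- 90% exact: 12.9% to 13.1%
- 98% exact: 17.5% to 17.7%, but with a width of about the same size
- 99% exact: 19.4% to 19.6%
- Wald 95%: 8.7%
- Wilson 95%: 14.7%

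None gives 18% together with a width of 15%. The sum 3% + 15% = 18% does match. It would arise if the whole width were placed above the estimate. The documents do not say so, and this remains an inference.

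**Comparison at the assumed rate.** The printed limit is 1 point below 19% and 5 points below 23%. The corrected limit of about 15% is 4 and 8 points below. The comparison still holds.

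**Dependence on the count.** Exact 95% upper limits at N = 35:

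| Positives | Upper limit | Below 19%? | Below 23%? |
|---|---|---|---|
| 0 | 10.0% | yes | yes |
| 1 | 14.9% | yes | yes |
| 2 | 19.16% | no, by 0.16 points | yes |
| 3 | 23.06% | no | no, by 0.06 points |

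At 2/35 the interval is 0.70% to 19.16%, a width of 18.5 points. So the width is 15 points or less only with 0 or 1 positive.

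**How often.** P(X ≤ 1) = (1 − p)^35 + 35p(1 − p)^34.

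- p = 3%: 0.344 + 0.373 = 0.717
- p = 5%: 0.166 + 0.306 = 0.472

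P(X ≤ 2) is 0.913 at 3% and 0.746 at 5%.

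**The case against.** The case for leaving this alone has four parts.

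1. *The error is harmless.* Correcting it moves the limit further from either comparator, N=35 rests on a width that is right, and the synopsis justifies N by width alone. The planned analysis computes its own interval from the observed count and never uses 18%. All of this stands. It limits the consequence, but a figure that contradicts the stated width still should not appear in both documents.

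2. *The sentence is conditional.* It describes the interval under an assumed 3% rate, and the protocol then says the final interval will use the observed rate. This stands too. The dependence on the count shows how fragile the planned precision is; it is not a second arithmetic error.

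3. *The comparison does not fail at 2 positives.* A reader might infer that the claim of lying below standard of care holds only with 0 or 1 positive. That is true against 19% but not against 23%, where 2/35 also qualifies. Even against 19% the miss is 0.16 points against a rounded percentage, so the documents do not settle on which side 2/35 falls.

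4. *The benchmark is not the reviewer's to choose.* A reader might take 19% as the intended rate, because Protocol 2.11.1 gives the paired 9% under the consensus margin definition that Appendix 1 adopts. That section ties only the MRI-guided group's 9% to that definition, and the synopsis gives 19% without one. Nor do the sample size sections say that their rate comes from this trial. A success criterion built on 19% would add a decision rule to a descriptive single-arm study. SAP 1.2.2 and 6.2 already describe surgeries in the past tense, so such a rule could itself be post hoc. The documents support neither step.

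**Conclusion.** The 18% is wrong on the plan's own inputs. The exact 95% upper limit is 14.9% at 1/35 and 15.1% at exactly 3%, so the printed figure is about 3 points too high in both Protocol 2.5.1 and SAP 1.2.3. The stated width, the sample size and the comparison with standard of care at a 3% rate all survive.

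Two omissions go with it. The comparator is unnamed although the protocol gives two candidates, and a result of 2/35 falls on different sides of them. The text also gives no sign of how readily the planned precision is missed: more than 1 positive occurs with probability 28% at a true 3%, and 53% at 5%, the edge of the plan's expected range.

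This rests on a two-sided 95% interval and on 35 patients with a margin assessment, as SAP 1.2.3 specifies. With fewer assessed the limits rise slightly: at 33 patients, 1 positive gives 15.8%.

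**What to change.** In Protocol 2.5.1 and SAP 1.2.3:

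- Replace 18% with about 15%, for example: *the exact 95% interval is about 0.1% to 15% (0.07% to 14.9% at 1/35)*.
- State which standard-of-care rate is meant, with its source and margin definition. The sponsor has to supply this; the rate should not be set at 19% by default.
- State that the 15% width and upper limit apply at about 1 positive in 35. List the upper limits for 0 to 3 positives (10.0%, 14.9%, 19.2%, 23.1%) and give the probability of at most 1 positive (72% at a true 3%, 47% at 5%).
- Add no success rule; the primary analysis stays an estimate with its exact interval.

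The cost is wording only, with no extra patients and no change of method. The SAP is at version 0.1 and is to be finalized before database lock, so it can be corrected there. The protocol supplied is dated 25 November 2022, while SAP 1.1 cites version 2.0 of 21 November 2023. The sponsor should check whether the figure persists in that version and use the amendment route in Protocol 4.3 if needed. The downside is a less favourable statement of how often the planned precision will be reached.

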### 2.5.2 Data Analysis

In general, all the variables will be descriptively analysed by visit (mean, median, standard deviation, minimum and maximum for continuous variables after normality check of distribution with Kolmogorov-Smirnov test, frequency distribution for categorical variables).

In particular, for the primary analysis PMR will be calculated when results of histopathological examination will be provided (results will be available within 14 days from the day of sample arrival at the pathological lab).

Moreover, 95% Confidence Interval (CI) of PMR will be presented.

All secondary endpoints will be evaluated in a descriptive way presenting the results by study visit, where appropriate.

All the analysis will be detailed in the Statistical Analysis Plan (SAP) which will be finalized in Version 1.0 before the Data Base Lock (DBL).

### 2.5.3 Safety Analyses

Safety will be monitored through vital signs, physical examination, laboratory parameters, and adverse events including assessment of relationship to the IP.

Summary table of AE details will also be reported including frequency, maximum intensity, relation to study treatment, seriousness, action taken, and outcome. Regarding relation: definite, probable, and possible is classified as "related" and unlikely and unrelated is classified as "unrelated" (see Section 3.6).

Safety data will only be handled descriptively.

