of confirming the safety and performance throughout the expected lifetime of the device, of ensuring the continued acceptability of identified risks and of detecting emerging risks on the basis of factual evidence. Since the BCL system is a new custom-made device, the aim of this investigational, post-market clinical investigation is to collect clinical data to confirm the safety and performance of the device in patients eligible for BCS in European countries.

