- 3) The BCL provides a localization cue (the hook wire) with which surgeons are familiar yet improves current practice because the wire placement does not require a separate procedure on the day of surgery, which can complicate surgical scheduling and cause patients pain [20].
- 4) The BCL is safe, quick, easy to use, and accurately localizes breast cancers [20].
- 5) The volume of breast tissue excised upon BCS with BCL is expected to be close or lower to the "ideal" resection volume [20].
- 6) As cosmetic outcome is negatively influenced by the percentage of breast volume excised, and by re-excision procedures [26], the BCL System is expected to improve cosmesis and patient satisfaction after breast-conserving surgery.

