**Table 22A. Summary of adverse events – AE occurrence**

**Safety Analysis Set**

|   |              | SAS
(N=XX) |
|---|--------------|-----------------------|
| Number of patients with at least one AE  | N (%) | X (XX.X)              |
| Number of patients with at least one related AE  | N (%) | X (XX.X)              |
| Number of patients with at least one serious AE  | N (%) | X (XX.X)              |
| Number of patients with at least one severe AE   | N (%) | X (XX.X)              |
| Number of patients who prematurely terminated the study due to an AE   | N (%) | X (XX.X)              |
| Number of deaths   | N (%) | X (XX.X)              |
| Number of AEs  | N     | X                     |
| Number of SAEs   | N     | X                     |
| Number of related* AEs   | N     | X                     |
| Number of severe AEs   | N     | X                     |
| Number of events   | N     | X                     |
| 
* Includes answers: Possible, Probable or Causal relationship
 
AE: Adverse Event
 PT: Preferred Term
 SAE: Serious Adverse Event
 SAS: Safety Analysis Set
 |              |                       |

|  |                           |                  |                |
|--|---------------------------|------------------|----------------|
|  | Form               | Form Nr.  | 1M-DMST-011-A3 |
|  | Statistical Analysis Plan | Page      | 79 of 116      |
|  |                           | Version # | 0.1            |

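### The study is meant to confirm safety but reports it as bare counts: add exact 95% intervals, because zero events in 35 patients leaves true rates up to 10.0% open

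*Protocol*

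**What the plan says.** **Aim.** Protocol 1.4 ends by giving the aim of the investigation as to "collect clinical data to confirm the safety and performance of the device in patients eligible for BCS in European countries". The secondary objective in protocol 2.2 is softer: "To evaluate the safety and tolerability of BCL". No threshold, hypothesis or detectable event rate is attached to either.

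**Analysis.** Protocol 2.5.3 says "Safety data will only be handled descriptively". Protocol 2.5.2 says of the secondary endpoints, which include safety, "All secondary endpoints will be evaluated in a descriptive way". The only interval planned in the protocol is for the primary endpoint: "Moreover, 95% Confidence Interval (CI) of PMR will be presented". SAP 6.2.1 makes that interval exact (Clopper-Pearson).

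**Safety output.** SAP 6.4.1 and 6.4.5 and the layouts in SAP 9.1 give patient counts with percentages and event counts. A typical row is "Number of patients with at least one related AE", shown as N (%). No safety row or column carries an interval. SAP 7 declares no change from the protocol's analysis.

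**Conclusion expected.** Protocol 4.14 requires the final report to give the investigator's summary opinion on performance and safety. Protocol 2.11.5 lists monitoring during this study as the step taken against infection due to the device, pneumothorax and inaccurate localization.

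**The concern.** A percentage without an interval says least when the count is zero or one, which is where a small study of a low-risk device is likely to end. The report could print 0 (0.0%) for related or serious events beside an aim worded as confirming safety, with nothing on the page to show which event rates the data exclude.

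The background text shows how that step can be taken. Protocol 2.11.1 reports no adverse events in a pilot of 19 subjects and then lists the device as safe among the anticipated benefits. No limit is attached to that result.

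At stake is the wording of the safety conclusion. The data collected would be the same either way.

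**Working it through.** **Inputs.**
- N = 35: enrolled, in the protocol synopsis; operated with a margin assessment, in SAP 1.2.3.
- The safety set holds operated patients only, and withdrawals are not replaced (protocol 2.5.4, 2.5.5). The safety-set N may therefore fall below 35 under the protocol.
- Method: exact Clopper-Pearson, as already specified for the positive margin rate.

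**1. The plan's own figure.** At N = 35 and a rate of 3% (x = 0.03 × 35 = 1.05), the two-sided 95% interval is 0.09% to 15.14%, a width of 15.05%. The stated width of 15% reproduces, so the method is the intended one. The stated upper limit of 18% does not reproduce. It equals 3% + 15%, whereas the exact limit is 15.1% (14.9% with x = 1). That is a separate correction.

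**2. Upper limits for safety proportions.** For zero events the two-sided 95% limit is 1 − 0.025^(1/n) and the one-sided 95% limit is 1 − 0.05^(1/n). For x > 0 the limits are beta quantiles.

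| Result | Two-sided 95% upper limit | One-sided 95% upper limit |
|---|---|---|
| 0/35 | 10.0% | 8.2% |
| 1/35 | 14.9% | 12.9% |
| 2/35 | 19.2% | 16.9% |
| 3/35 | 23.1% | 20.7% |
| 0/30 (assumes five patients do not reach surgery) | 11.6% | 9.5% |

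The pilot result, 0/19, has a two-sided limit of 17.6%.

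**3. Chance of seeing no case of a given harm in 35 patients:** (1 − p)^35.

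| True rate p | Chance of no case |
|---|---|
| 0.5% | 83.9% |
| 1% | 70.3% |
| 2% | 49.3% |
| 3% | 34.4% |
| 5% | 16.6% |

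The even-odds rate is 1 − 0.5^(1/35) = 1.96%. An 80% chance of at least one case needs a true rate of 1 − 0.2^(1/35) = 4.5%.

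**4. Against the protocol's own rates (2.11.3).**
- Bleeding needing return to theatre, 0.5–1%: 70–84% chance of no case.
- Anaphylaxis to contrast, 0.001–0.01%: above 99%.
- Failed localization with the earlier supine-MRI technique, 1/67 = 1.5%: 59%.
- Pneumothorax and infection from the device: no rate is given, so no figure can be computed without an assumption.

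**5. The numerator for related events.** Protocol 2.5.3 counts possible, probable and definite as related, and unlikely and unrelated as not. The SAP 9.1 footnote to the adverse-event summary counts possible, probable and causal. The derived-variable text in SAP 6.4.1 also admits none and unlikely, which would make every assessed event related. An interval on that row means nothing until the definition is settled.

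**The case against.** The case against is substantial.

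- The formal objective is to evaluate safety, and the word confirm in protocol 1.4 follows the regulatory language set out just before it.
- Descriptive safety reporting is normal for a secondary objective in a single-arm study of this size.
- The SAP goes beyond totals. It tabulates events by relationship, severity and seriousness, and lists each event with outcome and causality. At about 35 patients, case review carries much of the information.
- N and n are printed, so a reader can compute the limit.
- A separate US trial with more than 400 subjects is studying safety and effectiveness.
- An interval detects no additional event.

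Most of this stands, and it limits the point to presentation and wording. No hypothesis test or larger sample is called for. It does not remove the gap. Protocol 1.4 states the aim as this study's own, the report must give an opinion on safety, and the method that would qualify that opinion is already specified for another proportion. An exact interval is itself descriptive.

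Two stronger readings are tempting. A reader might infer that the plan treats few or no events as proof of safety. No such rule appears in either document, and the pilot statement in 2.11.1 is background and does not say how this trial's data will be interpreted. A reader might also infer that most serious harms would be missed. That holds only for a single harm with a true rate below about 2%. The bleeding rate of 0.5–1% is listed as a risk of the surgery, so missing it says little about the device, and the device's own pneumothorax and infection rates are not given.

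**Conclusion.** The point holds as a cheap improvement to a stated analysis choice. Safety is described in one place as something to confirm, it is reported without any upper limit, and zero events in 35 would leave true rates up to 10.0% open (two-sided; 8.2% one-sided). Bare zeros could be over-read; the documents do not show that they will be.

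The figures assume 35 patients in the safety set and independent events. Fewer operated patients widen the limits, to 11.6% at 30. They apply to operated patients only. The SAP cites protocol version 2.0, which was not available for this check. The protocol text used here is version 1.0 with the German amendment, so the wording should be checked against the current version before it is edited.

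**What to change.** 1. In SAP 6.4.1, define a related event as possible, probable or causal, matching the table footnote and the recorded response categories, and align protocol 2.5.3 with the same terms. This comes first.
2. In SAP 6.4.1 and 6.4.5 and the matching layouts, add exact two-sided 95% Clopper-Pearson intervals for the proportion of patients with at least one related event, at least one serious event, at least one device deficiency, pneumothorax, and infection. The deficiency table is laid out by visit, so it needs one row for any visit. List the coded terms that count as infection before database lock.
3. Use the actual safety-set N, and print the interval when the count is zero (for 0/35: 0 to 10.0%).
4. Change protocol 2.5.3 to *descriptively, with exact 95% confidence intervals for key safety proportions*. In 1.4, replace confirm with *estimate* or *describe* for safety.
5. Optional: in 2.11.1, state the pilot result as 0/19 with its upper limit of 17.6%.

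The cost is a few table cells, a few lines of text and a less favourable safety statement. No new data or patients are needed. The SAP is at version 0.1 and is to be finalized before database lock, so it can take the change.
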